11. DOSE MODIFICATIONS

11.1 Dose Modifications for Adverse Reactions

Interrupt IMBRUVICA therapy for any Grade 3 or greater non-hematological, Grade 3 or greater neutropenia with infection or fever, or Grade 4 hematological toxicities. Once the symptoms of the toxicity have resolved to Grade 1 or baseline (recovery), IMBRUVICA therapy may be reinitiated at the starting dose. If the toxicity reoccurs, reduce dose by one capsule (140 mg per day). A second reduction of dose by 140 mg may be considered as needed. If these toxicities persist or recur following two dose reductions, discontinue IMBRUVICA.

The dose of ibrutinib will be modified according to the dose modification guidelines in the table below if any of the following toxicities occur:

Parameter for which dose is being modified	Dose modification duration	Dose restarting parameters	Dose to be restarted	Comments
Grade 3 ANC (<1,000/ μ L) with an associated temperature of $\geq 38.5^{\circ}\text{C}$	Hold ibrutinib	Restart after 7 days provided ANC $\geq 1,000/ \mu\text{L}$ and patient is afebrile for at least 72 hrs.	Level -1	If toxicity is felt to be due to ibrutinib
Grade 4 ANC (<500/ μL) for more than 7 days	Hold ibrutinib	Restart after 14 days provided ANC $\geq 500/ \mu\text{L}$ for at least 7 days	Level -2	If toxicity is felt to be due to ibrutinib
Grade 3 thrombocytopenia (<50,000/ μL) in the presence of Grade ≥ 2 bleeding events	Hold ibrutinib	Restart after 14 days provided platelet count $\geq 50,000/ \mu\text{L}$ and no bleeding for at least 7 days	Level -2	If patient is on concomitant anticoagulation therapy, stabilize the anticoagulation therapy (if it was restarted) before ibrutinib is restarted
Grade 4 thrombocytopenia (<25,000/ μL)	Hold ibrutinib	Restart after 14 days provided platelet count $\geq 50,000/ \mu\text{L}$ for at least 7 days	Level -2	
Grade 3 or 4 nausea, vomiting, or diarrhea if persistent, despite optimal anti-emetic and/ or anti-diarrheal therapy	Hold ibrutinib	Restart after 14 days provided toxicity is at grade 2 or lower for at least 7 days	Level-2	Acute or chronic GVHD may cause nausea, vomiting, diarrhea and needs to be ruled out. If toxicity is attributed to GVHD and resolves drug can be restarted at dose level -1. Similarly, diarrhea can be due to Clostridium difficile colitis-if yes, no dose

Parameter for which dose is being modified	Dose modification duration	Dose restarting parameters	Dose to be restarted	Comments
				reduction may be necessary

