Any other Grade 4 or unmanageable Grade 3 toxicity attributed to ibrutinib	Hold ibrutinib	Discontinue drug (level -3)	Not applicable	None

Dose Levels:

- Dose level 0 = 420 mg po qd
- Dose level -1 = 280 mg po qd
- Dose level -2 = 140 mg po qd
- Dose level -3 = discontinue drug

For patients starting with 140 mg qd (due to concomitant moderate CYP3A inhibitor or azole use as outlined in section 11.2)

- Dose level 0 = 140 mg po qd
- Dose level -1 = 70mg po qd
- Dose level -2 = 70 mg po qod
- Dose level -3 = discontinue

If a patient was on 140 mg po qd (due to concomitant azole use) and then stopped azole, the dose will be increased to 420 mg po qd. This will not be considered a dose escalation.

For patients starting with 70 mg qd (due to concomitant Posaconazole use as out lined in section 11.2)

- Dose level 0 = 70 mg po qd
- Dose level -1 = 70 mg po qod
- Dose level -2 = discontinue

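### Section 11.1 does not say whether a short afebrile Grade 4 neutropenia attributed to ibrutinib is discontinued or may restart at the starting dose

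*Combined protocol and SAP*

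**What the plan says.** Section 11.1 of the combined protocol and SAP gives two sets of instructions.

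The opening paragraph begins "Interrupt IMBRUVICA therapy for any Grade 3 or greater non-hematological" and goes on to include "or Grade 4 hematological toxicities", with no condition on duration. Its restart rule is: "Once the symptoms of the toxicity have resolved to Grade 1 or baseline (recovery), IMBRUVICA therapy may be reinitiated at the starting dose". A recurrence lowers the dose by 140 mg.

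The table that follows is introduced in mandatory terms. The rows that matter here are:

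- First ANC row: labelled Grade 3, below 1,000/µL, "with an associated temperature of" 38.5 °C or more. Restart at Level -1.
- Second ANC row: Grade 4, below 500/µL, "for more than 7 days". Restart at Level -2, after 14 days, once the ANC has been at least 500/µL for at least 7 days.
- Grade 4 thrombocytopenia row: no duration or response condition. Restart at Level -2.
- GI row: "Grade 3 or 4 nausea, vomiting, or diarrhea if persistent, despite optimal anti-emetic and/ or anti-diarrheal therapy". Restart at Level -2.
- Last row: "Any other Grade 4 or unmanageable Grade 3 toxicity attributed to ibrutinib". Discontinue.

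The dose ladders below the table set Level -2 at 140 mg daily for a 420 mg start, 70 mg every other day for a 140 mg start, and discontinuation for a 70 mg start.

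**The concern.** Two of the three named rows that cover a Grade 4 event (ANC and GI) carry a condition that leaves part of the event outside the row. The platelet row does not. Taken at its word, the last row collects what is left over and stops the drug. The milder form of the event would then be treated more severely than the worse form, and differently from the opening paragraph.

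The trial runs at several centers, and section 26.4 does not permit deviations except to remove an immediate hazard. After the same short episode, one center could stop ibrutinib for good and another could resume the starting dose, each believing that it had followed the protocol. Safety and tolerability of ibrutinib is a secondary objective, and section 25.1 tabulates reasons for discontinuation. Part of that table could then reflect how a site read section 11.1.

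**Working it through.** The plan gives no figure on this point, so there is none to reproduce. The check traces a first, ibrutinib-attributed episode through the text.

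**1. Which row applies?** A Grade 4 ANC with a temperature of 38.5 °C or more also meets the numeric limit of the first ANC row, so it has a row even though the label says Grade 3. One lasting more than 7 days has the second ANC row. What remains is a Grade 4 ANC of 7 days or less with a temperature below 38.5 °C. No named row covers it.

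**2. What dose follows the hold?**

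| Starting dose | Short event, last row read literally | Short event, opening paragraph | Event over 7 days, its own row |
|---|---|---|---|
| 420 mg daily | 0 | 420 mg daily | 140 mg daily |
| 140 mg daily | 0 | 140 mg daily | 70 mg every other day (mean 70/2 = 35 mg per day) |
| 70 mg daily | 0 | 70 mg daily | 0 (Level -2 is discontinuation) |

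On the first two ladders the literal reading puts the short event below the long one. On the third the two are equal, and only the conflict with the paragraph is left.

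**3. GI events.** Attributed Grade 4 nausea, vomiting or diarrhea that responds to therapy falls outside the GI row. The table above applies to it in the same way, with persistent GI toxicity in the last column.

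**4. Recovery criteria.** If the paragraph governs the short event, restart needs Grade 1 or baseline. The table puts Grade 3 below 1,000/µL, and entry to ibrutinib requires an ANC of at least 1.0 × 10⁹/L, so the threshold is at least 1,000/µL. After the longer event, 500/µL held for 7 days is enough. A patient settled at 600 to 900/µL could restart after the long event but not after the short one.

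**5. Recurrence.** A 140 mg cut gives 420 − 140 = 280 mg, which is Level -1. From 140 mg it gives 140 − 140 = 0, although that ladder has two lower dose levels. From 70 mg it cannot be applied.

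**6. Limits on the conflict.** Every reading holds the drug at first detection. Section 21.1 withdraws treatment when an adverse event prevents dosing for more than 28 continuous days, so the conflict concerns holds of 28 days or less. To illustrate for one hypothetical patient, assume a hold of 7 to 28 days that is lost on every reading, and treatment planned to day 365. For an event seen at the first weekly count (day 67 or 97), 365 − 67 = 298 and 365 − 97 = 268 days remain. Stopping for good then costs a further 268 − 28 = 240 to 298 − 7 = 291 planned days. At month 9 (day 274, at 30.4 days per month) 365 − 274 = 91 days remain, and the further cost is 91 − 28 = 63 to 91 − 7 = 84 days.

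**The case against.** The strongest reply is that the last row refers to other kinds of toxicity. On that reading the paragraph is the default, the ANC and GI rows pick out the worse episodes, and the last row handles toxicities not named above it. Every sentence then has a job and the inversion disappears. The literal reading, by contrast, leaves the paragraph's restart rule with no attributed Grade 4 event to govern. This reading is plausible, but the text does not state it. Each row is defined by a grade plus a condition, so a site can just as reasonably take the last row to mean any Grade 4 event that misses those definitions. The reading also leaves one conflict standing. For an attributed Grade 4 non-hematological toxicity of an unlisted type, the paragraph allows restart at the starting dose while the last row discontinues.

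A second reply is that the table is mandatory and the paragraph only permissive, so the table wins. That is good evidence of precedence for events that the table lists. It does not settle whether the short event is one of them.

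A third reply is that stopping ibrutinib after a Grade 4 GI event attributed to it is defensible even if the event responds to therapy. That stands. The GI gap is a gap in the text, and the restart dose is for the clinical team to decide.

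A reader might also infer that many patients would lose most of their treatment. The documents do not support that. Section 6.3.3 lists neutropenia (hematologic malignancies) and diarrhea (chronic GVHD) among Grade 3 or 4 events seen in more than 5% of patients, but gives no Grade 4 rate. Section 13.1 permits neutrophil growth factors. The day counts are calendar time for one patient.

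**Conclusion.** The point holds as a conflict between stated dosing rules. For a first afebrile Grade 4 ANC of 7 days or less attributed to ibrutinib, section 11.1 supports either discontinuation or restart at the starting dose, and does not expressly say which. On the 420 mg and 140 mg ladders, the literal reading is also harsher than the action for the longer event.

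It would go too far to say that the protocol orders discontinuation for the short event, that the inversion exists on all three ladders, or that responding GI events ought to resume at full dose. No effect on the primary endpoint, sample size or number of affected patients is claimed. The conclusion rests on attribution to ibrutinib, a first episode, and a hold of 28 days or less. It is worth correcting because sites need one answer and the correction is cheap.

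**What to change.** Three wording changes to section 11.1, for the clinical team to confirm:

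- (a) Reword the last row: *Grade 4 toxicity of a type not listed above, or unmanageable Grade 3 toxicity of a type not listed above, attributed to ibrutinib.*
- (b) Add one sentence: *The table overrides the opening paragraph for the events it lists; the paragraph governs shorter or treatment-responsive episodes of those toxicity types, and a recurrence steps down one level on the patient's own ladder.*
- (c) Set the ANC recovery criterion so that the short event does not need a higher count than the event of more than 7 days.

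The clinical team should confirm in particular that (b) gives the restart dose it wants for Grade 4 GI toxicity that responds to therapy. It should also say what happens to an unmanageable Grade 3 fall in platelets without bleeding, or in ANC without fever or infection. Under (a) these leave the last row, and the opening paragraph does not cover them.

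The cost is a small wording amendment. Data collection and sample size do not change.

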11.2 Dose Modifications for Use with CYP3A Inhibitors

Avoid co-administration with strong or moderate CYP3A inhibitors and consider alternative agents with less CYP3A inhibition.

Concomitant use of strong CYP3A inhibitors which would be taken chronically (e.g., ritonavir, indinavir, nelfinavir, saquinavir, boceprevir, telaprevir, nefazodone) is not recommended. For short-term use (treatment for 7 days or less) of strong CYP3A inhibitors (e.g., antifungals and antibiotics) consider interrupting IMBRUVICA therapy until the CYP3A inhibitor is no longer needed.

Reduce IMBRUVICA dose to 140 mg if a moderate CYP3A inhibitor must be used (e.g., fluconazole, darunavir, erythromycin, diltiazem, atazanavir, aprepitant, amprenavir, fosamprevir, crizotinib, imatinib, verapamil, and ciprofloxacin).

Patients taking concomitant strong or moderate CYP3A inhibitors should be monitored more closely for signs of IMBRUVICA toxicity.

As most post-HCT patients are expected to be on azoles (fluconazole, voriconazole or lower doses of posaconazole as outlined in the table below) until day 100 after HCT, the dose of IMBRUVICA will be 140 mg per day. For patients receiving higher doses of posaconazole as outlined below, the dose of IMBRUVICA will be 70 mg per day. Once these agents are stopped, the dose will be escalated to 420 mg per day.

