2.4 Dose Modifications for Use with CYP3A Inhibitors		
Recommended dose modifications are described below [see Drug Interactions (7.1)]:		
Patient Population	Coadministered Drug	Recommended IMBRUVICA Dose
B-Cell Malignancies	
 Moderate CYP3A inhibitor Voriconazole 200 mg twice daily Posaconazole suspension 100 mg once daily, 100 mg twice daily, or 200 mg twice daily 	140 mg once daily Interrupt dose as recommended [see Dosage and Administration (2.3)].
	
 Posaconazole suspension 200 mg three times daily or 400 mg twice daily Posaconazole IV injection 300 mg once daily Posaconazole delayed-release tablets 300 mg once daily 	70 mg once daily Interrupt dose as recommended [see Dosage and Administration (2.3)].
	
 Other strong CYP3A inhibitors 	Avoid concomitant use. If these inhibitors will be used short-term (such as anti-infectives for seven days or less), interrupt IMBRUVICA.

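### Section 11.2 sends every patient to 420 mg once the azole stops, with no exception for a patient already reduced for toxicity

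*Combined protocol and SAP*

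**What the plan says.** Section 11.2 expects most patients to be on an azole until about day 100. It sets ibrutinib at 140 mg daily with fluconazole, voriconazole or lower-dose posaconazole, and at 70 mg daily with higher-dose posaconazole. It ends: "Once these agents are stopped, the dose will be escalated to 420 mg per day". No condition is attached.

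Section 11.1 has a parallel sentence, for a patient who "was on 140 mg po qd (due to concomitant azole use) and then stopped azole, the dose will be increased to 420 mg". It adds that this increase does not count as an escalation. There is no matching sentence for a patient on the 70 mg posaconazole ladder.

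Section 11.1 also holds the toxicity rules. Its opening text says that after a first event has resolved, "IMBRUVICA therapy may be reinitiated at the starting dose". A table follows, introduced by "The dose of ibrutinib will be modified according to the dose modification guidelines in the table below if any of the following toxicities occur", and most of its rows name a restart level. Below the table are three ladders: no inhibitor, 140 mg start and 70 mg start. Nothing says how a level reached on one ladder translates to another.

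Section 11.3 recommends 140 mg daily for Child-Pugh class A, without reference to azole use. Section 10 excludes only class C by name.

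**The concern.** Stopping the azole is the planned course for most patients, so most will meet this rule. The uncommon part is having been reduced for toxicity beforehand. For such a patient, the final sentence of Section 11.2, taken at its word, undoes a reduction that the Section 11.1 table required.

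One table row that leads to Level -2 is Grade 3 thrombocytopenia with bleeding, and Section 13.4 records fatal bleeding on this drug. A site that prefers a lower dose would be departing from the written rule. Section 26.4 bars deviations except to remove an immediate hazard, and Section 19 requires written approval for them. Sites could therefore dose the same patient differently.

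**Working it through.** The plan gives no figure to reproduce. The check sets the dosing rules side by side and takes ratios of nominal dose.

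**Ladders (Section 11.1)**

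| Level | No inhibitor | 140 mg azole ladder | 70 mg posaconazole ladder |
|---|---|---|---|
| 0 | 420 mg daily | 140 mg daily | 70 mg daily |
| -1 | 280 mg daily | 70 mg daily | 70 mg every other day |
| -2 | 140 mg daily | 70 mg every other day | discontinue |
| -3 | discontinue | discontinue | none listed |

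**Literal reading of Section 11.2.** Every dosed patient goes to 420 mg. The comparator is the no-inhibitor dose at the same toxicity level, so both sides are without an inhibitor.

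- Level -1, from either inhibitor ladder: 420 / 280 = 1.5.
- Level -2, from the 140 mg ladder: 420 / 140 = 3.
- Level -2, from the 70 mg ladder: the patient is off drug, so there is no dose to raise.

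**Narrow reading.** The two sentences before the escalation sentence set 140 and 70 mg, which are Level 0 doses, and the Section 11.1 sentence is limited to 140 mg daily. On this reading the rule covers Level 0 only, and a patient on 70 mg daily or every other day for toxicity has no stated dose after the azole stops.

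**The upward step is not itself the error.** The nominal dose rises under any sensible rule because the inhibitor is gone. On the 140 mg ladder, Level 0 rises by 420 / 140 = 3. With the level carried over, Level -1 rises by 280 / 70 = 4, and Level -2 by 140 / 35 = 4, taking 70 mg every other day as 35 mg a day. The literal rule gives 420 / 70 = 6 and 420 / 35 = 12.

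**Table rows leading to reduction.** Of five rows that name a restart level, one (Grade 3 neutropenia with fever) gives Level -1. Four give Level -2: Grade 4 neutropenia, Grade 3 thrombocytopenia with bleeding, Grade 4 thrombocytopenia, and persistent Grade 3-4 gastrointestinal toxicity. The comments narrow this. Gastrointestinal toxicity attributed to GVHD restarts at Level -1, *C. difficile* colitis may need no reduction, and both neutropenia rows apply only if attributed to ibrutinib.

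**Time available, assuming the azole stops on day 100.** Ibrutinib starts on days 60 to 90, so time on the azole dose is 100 - 90 = 10 to 100 - 60 = 40 days.

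- A Level -1 restart after a 7-day hold needs the hold to begin by day 100 - 7 = 93.
- A Level -2 restart after a 14-day hold needs it by day 100 - 14 = 86. That leaves at most start days 60 to 85, or 26 of 31.
- The Grade 4 neutropenia row needs more than 7 days below threshold first, so its window is shorter.
- A later azole stop widens all of these.

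**Monitoring around the switch (Section 20).** Weekly laboratory tests last 28 days from start. They have ended by day 100 for starts on days 60 to 72 (72 + 28 = 100; 13 of 31 days) and run past it for days 73 to 90 (18 of 31). Toxicity assessments are weekly to the later of day 100 and four weeks on drug, then monthly to month 12. Laboratory tests continue monthly to month 6.

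**Child-Pugh A.** On a standard azole, Sections 11.2 and 11.3 both give 140 mg. After the azole stops they give 420 and 140 mg: 420 / 140 = 3.

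**The case against.** The best defence is that the escalation sentence only removes an interaction adjustment. It follows two Level 0 doses, Section 11.1 limits its version to 140 mg daily, and that section says the step is not an escalation. Because the ladders share level labels, carrying the level across is the natural inference. This is a fair reading, and many clinicians would adopt it. It still leaves the reduced patient's dose unwritten, and Section 11.2 itself carries no such limit. A stated rule that gives the wrong dose when followed as written is more than missing detail.

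The safeguards also count. Toxicity assessments continue after the switch, holds apply if toxicity recurs, and Section 24.3 schedules two safety calls a month. They reduce the risk without removing it. For starts on days 60 to 72, weekly assessment ends at day 100, just when the dose is expected to rise. Holds act only after a recurrence. The other monitoring instruction, "Patients taking concomitant strong or moderate CYP3A inhibitors should be monitored more closely for signs of IMBRUVICA toxicity", does not reach a patient who has stopped the inhibitor.

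On Child-Pugh A the objection largely succeeds. Section 11.3 is written for that population and most naturally governs, so one sentence of priority is enough.

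**Conclusion.** The point stands as a minor safety fix. Followed as written, Section 11.2 puts a patient reduced on the 140 mg azole ladder on 1.5 times (Level -1) or 3 times (Level -2) the no-inhibitor dose for the same level. Read narrowly, it gives no dose. The ratios assume that the level should carry over, which the documents do not state. The number affected is unknown and probably small, since it takes a toxicity reduction before the azole stops, and the opening text of Section 11.1 lets some events restart without one.

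Three stronger inferences are not supported:

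- A reader might take 1.5 and 3, or the 6- and 12-fold steps, as increases in exposure. They are nominal doses. Stopping an inhibitor lowers exposure, and the documents give no figures from which to work out the net change.
- A reader might infer an effect on the primary endpoint or on power. Nothing here bears on either.
- A reader might infer a matching defect when a patient already at 140 mg for toxicity begins a moderate inhibitor. Section 11.2 first asks that such inhibitors be avoided, then states a dose: "Reduce IMBRUVICA dose to 140 mg if a moderate CYP3A inhibitor must be used". The documents offer no benchmark showing that dose to be wrong for this patient.

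**What to change.** Amend Sections 11.1 and 11.2 to say that the toxicity level carries over when an inhibitor stops:

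- From the 140 mg ladder: Level 0 to 420 mg, Level -1 to 280 mg, Level -2 to 140 mg daily.
- From the 70 mg posaconazole ladder: Level 0 to 420 mg, Level -1 to 280 mg daily. Level -2 is discontinuation and stays so.

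Add to Section 11.3 that its 140 mg for Child-Pugh A takes priority over Section 11.2 after the azole stops.

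The cost is a few reworded sentences in an amendment, with no added visits or patients. The downside is that a few patients would receive less drug after azole stop than Section 11.2 now gives. The mapping uses only doses already in Section 11.1, but the sponsor's clinical team should confirm it. One reason is that, even with carry-over, the nominal step up on the 140 mg ladder is 4-fold for a reduced patient against 3-fold at Level 0.

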2.4 Dose Modifications for Use with CYP3A Inhibitors		
Recommended dose modifications are described below [see Drug Interactions (7.1)]:		
Patient Population	Coadministered Drug	Recommended IMBRUVICA Dose
B-Cell Malignancies	
 Moderate CYP3A inhibitor Voriconazole 200 mg twice daily Posaconazole suspension 100 mg once daily, 100 mg twice daily, or 200 mg twice daily 	140 mg once daily Interrupt dose as recommended [see Dosage and Administration (2.3)].
	
 Posaconazole suspension 200 mg three times daily or 400 mg twice daily Posaconazole IV injection 300 mg once daily Posaconazole delayed-release tablets 300 mg once daily 	70 mg once daily Interrupt dose as recommended [see Dosage and Administration (2.3)].
	
 Other strong CYP3A inhibitors 	Avoid concomitant use. If these inhibitors will be used short-term (such as anti-infectives for seven days or less), interrupt IMBRUVICA.

